10 STUDY PROCEDURES

10.1 Enrollment

This research study will be explained in lay terms to each potential research subject. As the part of the informed consent process outlined in CFR Title 21 Part 50, the investigator or physician listed on the FDA 1572 form will conduct a face-to-face meeting with the study candidate to review all of the required elements of informed consent. The potential study subject will sign an informed consent form before undergoing any screening study procedures. Once the informed consent process is complete, the subject is considered enrolled in the study. All enrolled subjects will be assigned a unique subject number and their disposition must be accounted for at the end of the study.

10.2 Screening Visit

The pre-transplant visit (visit 1) will begin at the time consent is obtained until all eligibility criteria are available. Subjects can be approached regarding potential study participation while on the organ transplant waiting list, however, the consent process must take place within 60 days of transplant. If the subject is consented on the day of transplant, it is at the discretion of the Investigator to ensure there is sufficient time to appropriately consent the potential subject. If the subject was consented greater than 30 days prior to transplant, the individual obtaining consent must reaffirm the subject's willingness to participate. Refer to Appendix 1, Schedule of Events- Pre-Transplant to Day 4 Post Transplant.

During the screening period the study personnel will review the subject's medical record for previous and current medical history and record the subject's demographic information (age, gender, and race), medications, hematology, chemistry, fasting lipid panel, hemoglobinA1c, and urinalysis. A serum pregnancy test will be conducted on all female subjects of child-bearing potential. Blood, urine and tissue will be collected for research studies.

During the screening visit, data regarding the donor will be collected; this includes demographics (age, gender, and race), cause of death, serum creatinine, HLA, Blood Type, CMV and EBV. Refer to Appendix 5, Schedule of Events – Donor. A sample of spleen will be requested from the local center HLA departments of alloimmune assays.

10.3 Study Assessments

Subjects enrolled in this study will be followed for a minimum of 52 weeks post-transplant in order to assess the primary endpoint. Subjects in the Investigational Arm who are eligible and attempt tacrolimus withdrawal will be followed for at least 60 days following the withdrawal of tacrolimus. Subjects may be followed for up to 18 months (76 weeks) depending upon study completion.

Subjects will have blood, tissue and urine collected for research studies at the following timepoints:

- Visit 1 (Pre-Transplant to Day 4 Post-Transplant)
- Post-Transplant: Days 28, 84 and Weeks 28, 36, and 52.

Clinical safety will be monitored through routine physical examinations and appropriate laboratory assessments every 4 weeks for the duration of the study. During this period, subjects will have repeated clinical/laboratory evaluations, as specified in the Schedule of Events (Appendix 1 through 3, Schedule of Events- Recipient and Appendix 4 – Reduced Follow-Up Schedule of Events - Recipient).

Infusion Supervision

In addition to the study visits and procedures listed in Appendix 1-4, participants assigned to the Investigational Arm will receive a NULOJIX® (belatacept) infusion on days 5, 14, 28, 56 and 84 post-transplant. After 84 days, participants in the Investigational Arm will continue NULOJIX® (belatacept) infusions every 4 weeks throughout the duration of the study. The infusion will be administered in a center where full resuscitation facilities are immediately available and under close supervision of the investigator or infusion center staff. A history of each infusion and any adverse side effects will be recorded and reported to the SACCC using the appropriate case report forms. Vital signs (temperature, blood pressure, pulse, and respiratory rate) will be obtained prior to the start of each infusion and again at the end of the infusion. Additional vital signs will be obtained as clinically indicated. At the discretion of the investigator, the infusion may be discontinued if there is a severe reaction to the infusion.

Clinical Assessments

Assessments for the development of new adverse events, serious adverse events, infections, rejections, graft loss, hospitalizations, new onset diabetes, and malignancies will be completed at each study visit. All events will be reported using a designated electronic case report form (eCRF).

Evaluation of Hemoglobin A1c levels, urinalysis, hematology, chemistry, and pill counts will be obtained at Days 28, 84 and Weeks 28, 36, and 52. Additional time points are also specified during Year 2 of transplant (Appendix 3).

Infections could influence results of noninvasive testing. We will therefore record and report hospitalizations for infection. Less serious infections that are diagnosed and treated on an outpatient basis during the interval between visits and confirmed by pertinent cultures or serologic studies as per the local site, will be recorded at each study visit and reported using a designated case report form. Undocumented, patient-reported infections (e.g. URI) will not be reported. Relationships between test results and clinical endpoints independent of infections will then be determined in secondary analyses.

Pregnancy Testing

Women of child bearing potential (WOCBP) must use an effective method of birth control during the course of the study, in a manner such that risk of failure is minimized. Prior to study enrollment, WOCBP must be advised of the importance of avoiding pregnancy during trial participation and the potential risk factors for an unintentional pregnancy. The subject must sign an informed consent form documenting this discussion.

Pregnancy testing must be performed prior to enrollment and first dose of NULOJIX® (belatacept). The results of all pregnancy tests (positive or negative) recorded on the eCRF. All WOCBP MUST have a negative serum pregnancy test within 72 hours prior to receiving the first dose of the investigational product NULOJIX® (belatacept). The minimum sensitivity of the pregnancy test must be 25 IU/L or equivalent units of Human Chorionic Gonadotropin (HCG). If the pregnancy test is positive, the subject must not receive the investigational product, and must not be enrolled in the study. All WOCBP should be instructed to contact the investigator immediately if they suspect that they might be pregnant (e.g., missed or late menstrual period) at any time during study participation. Subjects who become pregnant will be referred to the National Transplant Pregnancy Registry (http://www.jefferson.edu/ntpr/).

For women who become pregnant while using CellCept® or within 6 weeks of discontinuing therapy, the healthcare practitioner should report the pregnancy to the Mycophenolate Pregnancy Reference Registry ([name]) and should strongly encourage the patient to

enroll in the pregnancy registry. The patient should also be apprised of the potential hazard of mycophenolate products to the fetus. The risks and benefits of CellCept/Myfortic should be discussed with the patient. In certain situations, the patients and her healthcare practitioner may decide that the maternal benefits outweigh the risks to the fetus.

If following initiation of study treatment, it is subsequently discovered that a subject is pregnant or may have been pregnant at the time of investigational product exposure, including during at least 56 days after product administration, the investigational product will be permanently discontinued.

Protocol-required procedures for study discontinuation and follow-up must be performed on the subject unless contraindicated by pregnancy (e.g., x-ray studies). Other appropriate pregnancy follow-up procedures should be considered if indicated. In addition, the investigator must report on the appropriate follow-up information regarding the course of the pregnancy, including perinatal and neonatal outcome. Infants should be followed for a minimum of 8 weeks. This pregnancy surveillance procedure includes male subjects who fathered a child while receiving study medication; however, male subjects do not need to discontinue study medication.

Viral Monitoring

The local center will monitor all subjects for CMV and BKV infection by quantitative PCR in the blood. This monitoring will take place at days 28 and 84, and at weeks 28, 52 and 76. The local center investigators will make all treatment decisions.

For Cause Biopsies - Renal

The center will perform a biopsy per the discretion of the Investigator in cases of increase in serum creatinine, proteinuria, or other clinical symptoms.

The local center will send the Pathology Core Lab ([name], UCSF) the following:

- 5 original stained slides (1-Trichrome or unstained, 1-PAS, 3 H&E) for histology reading.
- The site will send 1 SV40 and 1- immunohistochemistry C4d stained slides, if collected as standard of care.
- The remaining portion of the FFPE block will be stored at the local center and sent to the Core Pathology when requested for additional immunohistochemistry studies.

The local center will send the Molecular Core Lab ([name], University of Alabama) the following:

• 1 core in RNALater for gene expression, mRNA profiling studies.

Standard of Care or For Cause Biopsies- Pancreas

The center will perform standard of care biopsies which will be read by the local pathologist using Banff criteria. The data generated from the local center reading will be entered in the study database. In addition, once the local pathologist has completed their review of the pathology slides, the site will send the original stained slides (1-Trichrome or unstained, 3 H&E, including a C4d and/or SV40, if collected) used in that reading to the core pathology laboratory. The Pathology Core Laboratory will scan the slides into an Aperio Scan System, and return the slides back to the local center.

Glomerular Filtration Rate (GFR)

Glomerular Filtration Rate (GFR) will be estimated using the Chronic Kidney Disease Epidemiology Collaboration (CKD-EPI) equation and the MDRD 4 variable. Demographic characteristics; gender, age and race are required for calculation in addition to serum creatinine which will be collected as specified in the Schedule of Events (SOE). The equation will be calculated at the SACCC.

Neurological Assessment

All participants will undergo a neurological exam as specified in the SOE. Subjects will be evaluated by their local Neurology consult service for cases with a significantly abnormal exam.

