1.5.4 Incidence and Severity of Rejection and Anti- Donor Reactivity

These endpoints will be assessed at 52 weeks post-transplant. Biopsy grading and antibody assessments will be performed at the CTOT-15 Core Laboratories.

- 1. The incidence and severity of acute cellular rejection defined by the Kidney Banff 2007 criteria and Pancreas Banff 2011 criteria within the first 52 weeks.
- 2. The severity of first and highest grade of acute cellular rejection in the renal and pancreas biopsies
- 3. The incidence of humoral rejection in the renal and pancreas biopsies.
- 4. The prevalence of *de novo* anti-donor antibodies and anti-HLA antibodies.
- 5. The type of treatment of rejection.

1.5.5 Safety Outcome Measures

The following safety outcome measures will be assessed:

- 1. The incidence of death, graft loss, or undetectable c-peptide.
- 2. The incidence of all adverse events (AEs) and serious adverse events (SAEs).
- 3. The incidence of selected AEs and SAEs including:
 - Infections requiring hospitalization or systemic therapy,
 - BK and CMV viremia (local center monitoring),
 - EBV Infection (local center monitoring),
 - Malignancy.

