8.7 Modification or Discontinuation of Study Therapy

Study treatment may be prematurely discontinued at the discretion of the Investigator for any of the following reasons:

- 1. The subject is unwilling or unable to comply with the protocol.
- 2. The subject experiences graft failure.
- 3. Any clinical AE, laboratory abnormality or intercurrent illness, which in the opinion of the site PI indicates that continued treatment with study therapy is not in the best interest.
- 4. Pregnancy.
- 5. Two consecutive missed NULOJIX® (Belatacept) infusions.

Subjects who prematurely discontinue study treatment will be treated according to the site standard of care and followed until 52 weeks post-transplant. Please refer to Reduced Follow-Up Schedule (Appendix 4). If subjects discontinue study therapy beyond week 52, they will complete the visits outlined in Appendix 3 [Schedule of Events (Recipient) Post-Transplant (Year 2)]. If the subject is unable to return to the study center, the data associated with these visits may be obtained from the subject's local physician.

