11.4 Collection and Recording of Adverse Events

11.4.1 Collection Period

Adverse events will be collected from the time of first dose of study drug, until he/she completes study participation or until 30 days after he/she prematurely withdraws (without withdrawing consent) or is withdrawn from the study.

11.4.2 Collecting Adverse Events

Adverse events (including SAEs) may be discovered through any of these methods:

• Observing the subject.

- Questioning the subject in an objective manner.
- Receiving an unsolicited complaint from the subject.

In addition, an abnormal value or result from a clinical or laboratory evaluation can also indicate an adverse event, as defined in Section 11.3, *Grading and Attribution of Adverse Events*.

11.4.3 Recording Adverse Events

Throughout the study, the investigator will record adverse events and serious adverse events as described previously (Section 11.2, *Definitions*) on the appropriate eCRF regardless of the relationship to study therapy regimen or study procedure.

Certain adverse events occur commonly in this study population and will not be recorded as an adverse event, unless it meets the definition of a serious adverse event.

• Occurrence of upper respiratory infection, nasopharyngitis, bronchitis, diarrhea, constipation, nausea, vomiting, abdominal pain, hypocalcaemia, hypercalcemia, hypercholesterolemia, hypomagnesemia, hyperuricemia, edema, pyrexia, hematuria, proteinuria, dysuria, cough, dyspnea, arthralgia, back pain, hip pain, fracture, headache, dizziness, tremor, acne, insomnia, anxiety, depression, stomatitis/aphthous ulcers, wound complications, AVF thrombosis, neutropenia, renal impairment, renal artery stenosis, incontinence, hydronephrosis, hematoma, lymphocele, musculoskeletal pain, alopecia, hyperhidrosis, atrial fibrillation.

Elective hospitalizations or hospital admissions for the purpose of conduct of protocol mandated procedures are not to be reported as an SAE unless hospitalization is prolonged due to complications.

All adverse events must be recorded by the site on the appropriate AE/SAE *eCRF* within 5 business days of the site learning of the adverse event(s). Please refer to Section 11.5 for reporting of events meeting serious criteria.

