The protocol defines 28 secondary clinical endpoints. The endpoints are to be computed and summarized by treatment and, in a few cases, by day/week and treatment. With the exception of specific AEs and lab parameters, proportions or means will be estimated for each treatment arm and tested for treatment differences through the use of a statistical model. The particular model to be used depends on the scale of measurement of the endpoint. The accompanying table lists each endpoint and its measurement scale (continuous, dichotomous, and ordinal). All tests of significance in all analyses will be made at the 0.05 level.

Dichotomous measures of prevalence and incidence will be analyzed with log-binomial regression models, wherein treatment effects will be estimated as relative risk ratios; the reference group will be the tacrolimus-thymoglobulin subjects. The log-binomial model (rather than logistic regression) is applied for prevalence and incidence analyses because model-based estimates of relative risk (RR) are both more desirable and appropriate for non-Poisson events that are expected to occur more commonly than in 10% of the cases. In such cases, logistic regression-based odds ratio (OR) estimates are poor estimators of the relative risk³¹,³²,³³,³⁴. It may be appropriate to treat some of the dichotomous outcomes as censored data; if this is the case, we will obtain RR estimates by fitting Cox regression models to the data³⁵.

The single ordinal secondary outcome variable (Banff cell-mediated AR score) will be analyzed in a proportional odds model³⁶ which may include additional covariates and interaction terms, as appropriate.

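### The tested safety incidences have no time window, while length of follow-up depends on whether a subject stops study therapy early

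*Combined protocol and SAP*

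**What the plan says.** Section 1.5.5 opens its list with "The following safety outcome measures will be assessed" and gives no time limit for any item: the composite of death, graft loss and undetectable C-peptide, adverse events and serious adverse events, selected infections, and malignancy. The rejection endpoint in 1.5.4, just before it, is limited to 52 weeks. The safety rows of Table 9 are likewise open-ended. Those that are tested call for a proportion with a 95% confidence interval and log-binomial or Poisson regression, with no offset or person-time term.

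Under 11.4.1, adverse events are collected from the first dose "until he/she completes study participation". How long that lasts depends on several rules:

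- **Everyone (10.3):** "Subjects enrolled in this study will be followed for a minimum of 52 weeks post-transplant in order to assess the primary endpoint".
- **Upper limit, either arm (10.3):** "Subjects may be followed for up to 18 months (76 weeks) depending upon study completion".
- **Withdrawers, investigational arm only (10.3):** those who are "eligible and attempt tacrolimus withdrawal will be followed for at least 60 days following the withdrawal of tacrolimus".
- **Early stoppers (8.7, Appendix 4):** they are "treated according to the site standard of care and followed until 52 weeks post-transplant". Appendix 4 has no visit after week 52.
- **Stopping reasons (8.7):** five are listed, and one is "Two consecutive missed NULOJIX® (Belatacept) infusions".
- **Version 7.0 amendment:** further tacrolimus withdrawal is halted. Subjects stay on the schedule they were already following until study completion on August 31, 2016.

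On unequal follow-up, 13.2.2 offers one sentence: "It may be appropriate to treat some of the dichotomous outcomes as censored data". Cox regression would then be used. No outcome is named, and no Table 9 row lists it.

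**The concern.** A crude proportion with an event is a fair comparison only if both arms are watched for the same time. Here the time watched depends partly on something that happens after randomisation, namely whether the subject stops study therapy before week 52. If stopping is more common in one arm, that arm contributes fewer weeks between 52 and 76. Its risk of death, graft loss, serious adverse events, infection or malignancy then looks lower even when the true hazards are equal.

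The later weeks are not idle. Section 5.1 reports that all but one of the 14 belatacept lymphoproliferative cases in the earlier kidney trials arose within 18 months of transplant, although it does not say how many fell after month 12. The choice between a crude and a censored analysis is also left open in an open-label trial.

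**Working it through.** **Plan's own figure.** The only stated total that bears on follow-up is study duration: 21 months accrual + up to 18 months follow-up = 39 months, which reproduces. No power or precision figure is given for the safety comparisons.

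**Step 1: the 60-day rule.** Weaning starts at week 40 (day 280) and takes 4 to 8 weeks (Appendix 2, note 6).

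- Shortest: 280 + 28 + 60 = day 368, or 52.6 weeks.
- Longest: 280 + 56 + 60 = day 396, or 56.6 weeks.
- Minimum for everyone else: day 364, or 52 weeks.

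The excess is 0.6 to 4.6 weeks (1 to 9%), and only where follow-up would otherwise end at the minimum.

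**Step 2: the split by therapy status.** Early stoppers end at week 52; others may reach week 76. The gap is up to 24 weeks, and 24/52 = 46%.

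**Step 3: effect on a crude proportion.** Assume the same constant hazard in both arms. With p52 the incidence at 52 weeks, incidence at week T is p(T) = 1 − (1 − p52)^(T/52). If a share d of an arm stops early and all others reach week 76, the arm's expected proportion is d × p52 + (1 − d) × p(76). Both p52 and d are assumptions.

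| p52 | p(76) | d = 10% | d = 30% | d = 50% | Ratio, 30% v 10% | Ratio, 50% v 10% |
|---|---|---|---|---|---|---|
| 10% | 14.27% | 13.84% | 12.99% | 12.14% | 0.94 | 0.88 |
| 30% | 40.62% | 39.56% | 37.44% | 35.31% | 0.95 | 0.89 |
| 50% | 63.69% | 62.32% | 59.58% | 56.84% | 0.96 | 0.91 |

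Example for p52 = 10%: 0.3 × 10% + 0.7 × 14.27% = 12.99%, and 12.99/13.84 = 0.94.

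**Step 4: the 60-day rule on the same scale.** Suppose all follow-up stops at the minimum and every investigational subject withdraws on the longest taper. The ratio p(56.6)/p52 is then 1.08, 1.07 and 1.06 for p52 of 10%, 30% and 50%. If 30 to 50% withdraw, it is 1.02 to 1.04. On the shortest taper it is about 1.01.

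**Step 5: against the trial's precision.** With 6 of 30 events in each arm (20%), the standard error of the log risk ratio is √[2 × (1/6 − 1/30)] = 0.516. The 95% interval around 1.0 is exp(±1.96 × 0.516) = 0.36 to 2.75. With 50% v 10% stopping, the chance of a nominally significant result in the direction of the distortion is about 4 to 6%, against 2.5% with no distortion.

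**The case against.** Much of the case on the other side stands.

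- **The 60-day rule sets a minimum, not an end date.** A reader might infer from it that the investigational arm is systematically watched longer. The documents do not support that. Either arm may be followed to week 76, subject to a common calendar end that randomisation balances in expectation. Version 7.0 is dated June 28, 2016, which is 64 days before August 31. If the halt took effect about then, anyone already withdrawn would reach 60 days before study completion anyway.
- **Weeks 76 and 52 are not the follow-up of two arms.** At p52 = 20%, p(76)/p52 = 27.8/20 = 1.39, and a reader might take that as the possible bias between arms. No rule follows one whole arm to week 76 and the other to week 52.
- **Stopping is not confined to one arm.** Four of the five reasons in 8.7 can occur in both arms, and all are discretionary. Assuming no early stopping among controls would overstate the effect.
- **Version 7.0 does not move the investigational arm to Appendix 4.** It takes those subjects off the protocol regimen but keeps their existing schedules.
- **The plan partly foresees the problem.** Section 13.2.2 mentions censoring and Cox regression, and 13.1 ties most secondary outcomes to measurements through week 52.

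The last point does not close the gap. Section 13.1 says only most outcomes and concerns scheduled measurements, whereas safety events accrue continuously under 11.4.1. The sentence in 13.2.2 is conditional and names no outcome. Nor does listing Poisson regression imply person-time: 13.2.2 seeks relative risks, and its cited source is a modified Poisson method for binary data.

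**Conclusion.** The concern holds in a limited form. The tested safety incidences have no window and are planned as crude proportions, while follow-up depends on therapy status after randomisation. The main driver is week 52 against a possible week 76; the 60-day minimum matters little.

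Under equal constant hazards, early stopping of 10% v 30 to 50%, and all others reaching week 76, the spurious risk ratio is about 0.88 to 0.96. The stopping shares and incidences are assumptions. The effect shrinks if events cluster soon after transplant or if many subjects end before week 76. The net direction is unknown, because early stopping and the post-withdrawal minimum can pull in opposite directions.

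At 30 per arm the distortion is small beside the imprecision and is unlikely to change a significance statement. It is still an avoidable bias in the main safety estimates. The documents do not establish that the arms will in fact be observed for unequal total time; they show that the plan neither prevents this nor commits to adjusting for it.

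**What to change.** Three changes to 1.5.5, 13.2.2 and Table 9:

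1. **Make the censored analysis definite.** For each tested safety row, analyse time to first event from transplant, censored at the subject's last contact, by Cox regression or as events per person-time, using all follow-up. Under equal constant hazards the expected ratio is then 1.00.
2. **Add a common-window proportion.** Count events in all randomised subjects through the week-52 visit, including its ±5-day window. A hard cut at day 364 would lose in-window findings on days 365 to 369. Renal graft failure is defined by 90 consecutive days of dialysis dependency, so a day-364 cut would also lose any loss whose dialysis began after day 364 − 90 = 274, before weaning can start at day 280. Date renal graft loss to the start of the qualifying dialysis period, and say how the 90 days are confirmed when follow-up ends at week 52.
3. **Handle C-peptide openly.** Appendix 4 does not schedule it, so a common window equalises time but not ascertainment. State this, and report undetectable C-peptide separately with the number assessed per arm. The week-52 BKV test is also absent from Appendix 4 and needs a similar note.

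The cost is wording and one extra table. The crude proportion over all follow-up becomes descriptive. Visits, treatment and sample size do not change.

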8 STUDY THERAPY REGIMEN

The study therapy regimen includes:

Control Arm

- ◆ Induction: 5 day course of MEDROL® (methylprednisolone) or equivalent;
- Induction: Thymoglobulin® (Anti-thymocyte Globulin (Rabbit));
- Maintenance Immunosuppression: Prograf® (tacrolimus), or generic;
- Maintenance Immunosuppression: CellCept® (mycophenolate mofetil- MMF), or Myfortic® (mycophenolate sodium), or generic.

Investigational Arm

- ◆ Induction: 5 day course of MEDROL[®] (methylprednisolone) or equivalent;
- Induction: Thymoglobulin® (Anti-thymocyte Globulin (Rabbit));
- Maintenance Immunosuppression: NULOJIX® (belatacept);
- Maintenance Immunosuppression: Prograf® (tacrolimus), or generic;
- Maintenance Immunosuppression: CellCept® (mycophenolate mofetil- MMF), or Myfortic® (mycophenolate sodium), or generic.

[figure not shown]

Figure 2. CTOT-15 Study Therapy Regimen

Study T	herapy Dosage	
CATEGORY	DRUG	DOSING
Investigational Agent	NULOJIX ® (belatacept)	INVESTIGATIONAL ARM: Participants will receive NULOJIX [®] (belatacept) 10mg/kg on days 5, 14, 28, 56 and 84. After 84 days, subjects will receive belatacept at the maintenance dose of 5 mg/kg every 4 weeks until completion of the trial.
Induction Therapy	Medrol [®] methylprednisolone	BOTH STUDY GROUPS : Methylprednisolone will be administered at a target dose of 500 mg beginning on the day of transplant, and tapered to 250 mg day 1 post-transplant, 125 mg day 2 post-transplant, 60 mg day 3 post-transplant, and 30 mg day 4 post-transplant. IV methylprednisolone will be administered over no less than 30 minutes in accordance with the applicable product labeling.
Induction Therapy	Thymoglobulin® (Anti-thymocyte Globulin (Rabbit))	BOTH STUDY GROUPS: The Thymoglobulin® target dosage is 6mg/kg total over 3 to 4 days. The recommended route of administration is intravenous infusion using a high-flow vein. Thymoglobulin should be infused over a minimum of 6 hours for the first infusion and over at least 4 hours on subsequent days of therapy. The infusion will be monitored per the center practice/SOPs. Premedication with corticosteroids, acetaminophen, and/or an antihistamine 1 hour prior to the infusion will be given per center practice and may reduce the incidence and intensity of side effects during the infusion. Medical personnel should monitor patients for adverse events during and after infusion.

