Appendix 1: Schedule of Events – Pre-Transplant to Day 4 Post-Transplant (Visit 1)

Screening Assessments	Window
 Blood Type (A, B, O), Rh Factor HLA Typing (Class I: A, B, C, Class II: DR, DP, DQ) Peak PRA, Current PRA or cPRA (within 12 months prior to transplant), Crossmatch Hepatitis B, Hepatitis C, and HIV test results Last reported CMV (IgG, IgM and/or total CMV Ab) and EBV testing (IgG, IgM) Tuberculosis testing (within 12 months prior to transplant). If documentation is not present at the time of transplant, and the subject does not have any risk factors for TB, a TB-specific interferon gamma release assay (IGRA) may be performed. 	Retrospective data collection, no time limits unless specified. Repeat only if not available.
 Informed Consent and Assessment of Eligibility Demographics Medical History, Physical exam (BP, Pulse, Temperature, Respiration, Weight) Concomitant Medications Local Labs: Serum Pregnancy Test, Hematology Panel (CBC, differential, platelets), Chemistry 12-Panel / CKD-EPI equation, MDRD 4 variable, Serum Amylase, Serum Lipase, Fasting Lipid Panel (Total, HDL, LDL, Triglycerides), Hemoglobin A1c, Urinalysis 	Within 30 days prior to transplant, until time of transplant.
 Flow Cytometry (20mL blood in Cyto-Chex Tube) Intracellular Cytokine Staining – Viral Phenotyping (32mL blood in CPT Tube) Markers of Autoimmunity – PBMC (30mL blood in Green-top Tube) Markers of Autoimmunity – serum (5mL blood in Red-top Vacutainer) Gene Expression, mRNA profiling in blood (2.5 mL blood in PAXgene RNA tube) Cytokines and Growth Factors- serum (7mL blood in Red-Top Vacutainer) Serum Proteins – CTGF, TGFbeta (4.5mL blood in CTAD) Urine Proteins – CTGF, TGFbeta (supernatant) Gene Expression, mRNA profiling in urine (urine pellet) Non-HLA Ab, Anti-HLA Ab, DSA (5mL blood in Red-top Vacutainer) Genomics- gene polymorphisms (4mL in Lavender-top EDTA Vacutainer) Viral Monitoring by PCR (CMV, BKV, JCV, HHV6, HHV7) and Viral Assay Development (HHV3- varicella zoster, HHV6- roseola, HHV7- cofactor CMV, polyoma JC, WC, KI).(plasma from ICS sample) 	Within 48 hours prior to transplant
 Randomization (RhoRand System) Assessment of Events: AE/SAE Solumedrol®(Methylprednisone) : 500mg – Intraoperatively Thymoglobulin® (Anti-thymocyte Globulin – Rabbit) Prograf® (tacrolimus) CellCept® (mycophenolate mofetil) 	Day of Transplant
 Methylprednisolone 250 mg Thymoglobulin® (Anti-thymocyte Globulin – Rabbit) 	Day 1 Post-Transplant

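### The serum pregnancy test that Section 10.3 requires within 72 hours before the first belatacept dose is missing from the schedules, and the pregnancy rules around it disagree

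*Combined protocol and SAP*

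**What the plan says.** **The condition.** Section 10.3 (Pregnancy Testing) sets two test points: "Pregnancy testing must be performed prior to enrollment and first dose of NULOJIX® (belatacept"). It then makes the second a timed condition: "All WOCBP MUST have a negative serum pregnancy test within 72 hours prior to receiving the first dose" of the investigational product. The stated consequence is "If the pregnancy test is positive, the subject must not receive the investigational product, and must not be enrolled in the study".

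**The schedules.** Appendix 1 lists the serum pregnancy test among the Visit 1 local laboratory tests, with the window "Within 30 days prior to transplant, until time of transplant". Section 10.2 describes the same screening test: "A serum pregnancy test will be conducted on all female subjects of child-bearing potential". The post-transplant rows of Appendix 1 list no pregnancy test, and neither do Appendices 2, 3 and 4.

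**The first dose.** Section 8 gives belatacept at "10mg/kg on days 5, 14, 28, 56 and 84". Sections 8.1.2 and 10.3 and the day-5 column of Appendix 2 agree. Footnote 4 of Appendix 2 adds that the first dose comes roughly 24 to 48 hours after the last Thymoglobulin dose.

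**Stopping for pregnancy.** Section 8.7 includes pregnancy in a list that opens "Study treatment may be prematurely discontinued at the discretion of the Investigator for any of the following reasons". A later paragraph of Section 10.3 makes permanent discontinuation of the investigational product mandatory when pregnancy is discovered after treatment has begun. Section 11.6 says that a pregnant subject should be told to stop study medication.

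**The concern.** The 72-hour test is written as an absolute condition, yet the tables that sites use to plan visits and blood draws contain no test that could meet it for a day-5 dose. Section 10.3 itself sends sites to those schedules for laboratory evaluations. A test missed before dosing cannot be recovered afterwards, and the condition exists to prevent fetal exposure.

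The second problem is what follows a positive result. A qualifying test for a day-5 dose falls when the woman is already in the trial, so an instruction not to enroll her has no meaning at that point. Only the investigational arm receives belatacept. Any uncertainty about what happens to such a subject therefore falls on one arm of a trial with 30 per arm.

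Third, a site that finds a pregnancy during treatment reads one section that leaves stopping to the investigator and two that do not.

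**Working it through.** The plan gives no figure of its own here. The check is clock arithmetic, followed by a comparison of the texts.

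**Inputs**
- Limit: 72 h before the first dose (Section 10.3).
- Test window: day −30 to the time of transplant (Appendix 1).
- First dose: day 5 (Sections 8, 8.1.2 and 10.3; Appendix 2).
- Day count: the day of transplant is day 0, because Appendix 1 lists it separately from day 1 post-transplant.

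**Age of the scheduled test at a dose on day d**
- Latest permitted test: 24 × d hours nominal. Clock times widen this to between 24 × (d − 1) and 24 × (d + 1) hours.
- For d = 5: 24 × 5 = 120 h nominal; least 24 × 4 = 96 h; most 24 × 6 = 144 h.
- Earliest permitted test: (30 + 5) × 24 = 840 h, or 35 days.
- Earliest qualifying test for a day-5 dose: day 5 − 3 days = day 2.

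Even the shortest gap, 96 h, exceeds the limit by 24 h. If transplant were counted as day 1, the nominal gap would be 4 × 24 = 96 h and the smallest would approach 72 h. Appendix 1 does not count that way.

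**Effect of footnote 4.** Section 8 allows a Thymoglobulin course of 3 to 4 days, and Appendix 1 starts it on the day of transplant.

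| Last Thymoglobulin dose | First belatacept dose, 24–48 h later | Age of a test done at transplant |
|---|---|---|
| Day 2 (3-day course) | Day 3 to day 4 | Day 3: 72 h nominal (48–96 h); day 4: 96 h nominal (72–120 h) |
| Day 3 (4-day course) | Day 4 to day 5 | Day 4: 96 h nominal (72–120 h); day 5: 120 h nominal (96–144 h) |

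A day-3 dose could just be covered by a test taken at transplant. It would depart from the day-5 column, so these two timings also need reconciling.

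**Consequence of a positive test.** Section 10.1 treats a subject as enrolled once consent is complete. Appendix 1 places randomization on the day of transplant. A qualifying test on day 2 or later follows consent, randomization and transplant, so the enrollment consequence in Section 10.3 cannot be carried out.

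**Pregnancy found after treatment starts**

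| Section | Rule |
|---|---|
| 8.7 | Stopping study treatment is at the investigator's discretion |
| 10.3, later paragraph | The investigational product is stopped permanently |
| 11.6 | The subject should be told to stop study medication |

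These three cover the same situation and do not agree.

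**The case against.** The strongest reply is that the appendices are not the whole protocol. Section 10.3 orders a test before the first dose in operative text, and nothing forbids an unscheduled test between day 2 and day 5. Other required items, such as pill counts, also have no row in Appendix 2. This stands. A reader might infer that no woman treated on schedule can satisfy the rule, but the documents do not support that: only the listed test fails, and a site that acts on Section 10.3 complies.

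A reader might also infer that a randomized woman with a positive test would be dropped, biasing the comparison. The documents largely point the other way. The Reduced Follow Up entry in Study Definitions keeps randomized subjects who leave their regimen in the study. Section 8.7 follows those who stop early to week 52 under Appendix 4. Neither Section 9.1 nor the Premature Termination definition names pregnancy. What remains is that Section 10.3 does not say this for a positive pre-dose test and gives a consequence that cannot apply. No bias has been shown.

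It is also tempting to set Section 8.7 against the sentence in Section 10.3 barring the product after a positive test. That sentence concerns a woman not yet dosed, whereas Section 8.7 concerns stopping treatment already under way. The real conflict is with the later paragraph of Section 10.3 and with Section 11.6. One could argue that discretion over the multi-drug regimen can coexist with mandatory stopping of belatacept, since Section 10.3 separately weighs mycophenolate in pregnancy. Section 8.7 does not draw that distinction, and Section 11.6 refers to study medication as a whole.

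Finally, the amendment text sets study completion at August 31, 2016. With the 12-month minimum follow-up in the synopsis, transplants would have ended by about August 2015, so first doses have probably all been given. That is an inference. It changes the practical action but does not remove the inconsistency.

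**Conclusion.** The point holds as an omission from the schedules together with two inconsistencies in the text. For a day-5 dose the scheduled test is about 5 to 35 days old against a 3-day limit, and never less than 96 h old. This assumes that transplant is day 0 and that dosing follows the day-5 column; a day-3 dose under footnote 4 is the one case where a test at transplant might qualify.

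Only women of childbearing potential in the investigational arm are affected. The documents do not give their number; the arm's planned 30 subjects is the ceiling. No endpoint, power figure or estimate is shown to change. The matter is one of subject safety and of clear disposition of randomized subjects.

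**What to change.** 1. Reconcile Section 10.3 with Appendices 1 and 2, so that the test Section 10.3 already mandates appears in the schedule before the first infusion. Reconcile the day-5 dose with footnote 4 at the same time.
2. Limit the enrollment consequence in Section 10.3 to the pre-enrollment test. State that a randomized woman with a positive pre-dose test stays in follow-up, consistent with Study Definitions and Section 8.7, and in the analysis.
3. Make Sections 8.7, 10.3 and 11.6 agree on stopping in pregnancy. The sponsor decides which rule stands.
4. If all first doses have been given, compare the test dates on the eCRF, where Section 10.3 requires every pregnancy test result to be recorded, with the first-dose dates, and report any that fall outside the condition.

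The cost is one schedule row and some wording. The test is already required, so no new procedure or dispensing rule is added. The date check uses data that the protocol already collects.
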